### **5.7.2. Laboratory Tests**

Hematological, serum biochemistry, adrenal laboratories, and urine data and their changes (only for continuous laboratory parameters) from baseline will be summarized by visit.

Shift tables for hematology and biochemistry data will also be presented showing change in CTCAE severity grade from baseline to each visit. For parameters for which a CTCAE scale does not exist, shift tables will be presented showing change in results from baseline (normal, low and high [or abnormal]) to each visit (normal, low and high [or abnormal]).

Summary of abnormalities in laboratory variables pre-defined for safety monitoring will be done per the following Table 2.

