7.8. Urinalysis

Urinalysis will include analysis for pH, specific gravity, glucose, ketones, blood, protein, urobilinogen, bilirubin, nitrite, and leukocytes. These parameters will be measured at

Screening/Baseline on Visit 1, Week 12 (Visit 2), Week 24 (Visit 3), Week 36 (Visit 4), Week 48 (Visit 5), Week 60 (Visit 6), Week 72 (Visit 7), Week 84 (Visit 8), Week 96 (Visit 9) Week 108 (Visit 10), Week 120 (Visit 11), Week 132 (Visit 12), Week 144 (Visit 13 - End-of-Treatment/Premature Discontinuation), and at the Post-Treatment visit (6 weeks post discontinuation of study drug). These parameters will be analyzed by the central laboratory. Urine samples will also be collected and shipped to central laboratory for assessment of urine protein, creatinine, osmolality, and urinalysis. The Central Laboratory Manual should be consulted for collection, processing, and shipping details.

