10.4.3. Primary Variables – Safety

Vital signs (height, weight, systolic and diastolic blood pressure, radial pulse rate, and body temperature) and physical examination data will be listed and summarized by visit and overall. Where appropriate, changes from baseline at each visit will be summarized and tested by means of the paired t-test or a nonparametric alternative.

Adverse events will be classified using the MedDRA classification system. The severity of adverse events will be graded according to the CTCAE, Version 3.0, whenever possible.

The frequency of patients experiencing a specific adverse event will be tabulated by treatment period and for the whole study, categorizing events by body system, and MedDRA term. In the by-patient analysis, a patient having the same event more than once will be counted only once. Adverse events will be summarized by worst CTCAE grade within a patient.

Adverse events classified as CTCAE Grade 3 or higher; study-drug-related events; adrenal, hepatic, and renal events leading to special diagnostic evaluations; events leading to discontinuation from treatment; and SAEs will be considered with special attention.

No attempt will be made to reconcile data collected from the patient/caregiver-reported outcome instruments with adverse event reporting.

Hematological data will be summarized by treatment period and overall. Hematological data will be graded according to CTCAE severity grade. The frequencies of the worst severity grade observed will be displayed by worst CTCAE grade within a patient.

Serum biochemistry and urine data (including parameters for assessment of adrenal, hepatic, and renal monitoring – see [Section 6.3.1](#)) will be summarized by treatment period and overall. Values will be graded according to CTCAE severity grade, when applicable. For variables graded according to CTCAE severity grade, the frequencies of the worst severity grade observed will be displayed within a patient. For parameters for which a CTCAE scale does not exist, the frequency of patients with values below, within, and above the normal ranges will be summarized.

Urinalysis data will be listed and summarized by treatment period and overall, and will be checked for changes from baseline over time.

The results of an ultrasound to examine the kidneys and collecting system will be listed and abnormal results will be noted and investigated in terms of their relation to other relevant patient outcome measurement.

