**Table 2: Safety Monitoring Parameters and Actions to be Taken**

Organ System and Laboratory Parameter	Stop Study Drug Immediately, Confirm Abnormal Value, and Then Start Work-Up	Stop Study Drug After Confirming a Abnormal Value, and Then Start Work-Up	Continue Study Drug, Confirm Abnormal Value, and then Start Work-Up a
Hepatic			
Serum total bilirubin	≥Grade 3 (≥3.0 x ULN)	Grade 2 (1.5 – 3.0 x ULN)	---
Serum GGT	≥Grade 3 (≥5.0 x ULN)	Grade 2 (>2.5 – 5.0 x ULN)	---
Serum ALT			↑ of >150 U/L with stable or ↓ CK
Renal			
Serum cystatin C	>2.00 mg/L	>1.33 – 2.00 mg/L	---
Serum creatinine	≥Grade 2 (≥1.5 x ULN for age)	Grade 1 (>ULN – 1.5 x ULN for age)	---
Serum BUN	≥3.0 x ULN	≥1.5 – 3.0 x ULN	---
Urine protein: urine creatinine (spot)	---	>0.40 mg:mg	---
Urine protein: urine osmolality (spot)	---	>0.30 mg/L:mOsm/kg	---
Urine blood (by dipstick)	4+ (Large)	3+ (Moderate)	2+ (Small)
Serum electrolytes	Grade 3-4	Grade 2	Grade 1
Serum Na + , high	>155 mmol/L	>150 – 155 mmol/L	---
Serum Na + , low	<130 mmol/L	---	---
Serum K + , high	>6.0 mmol/L	>5.5 – 6.0 mmol/L	---
Serum K + , low	<3.0 mmol/L	---	---
Serum Mg 2+ , high	>1.23 mmol/L	---	---
Serum Mg 2+ , low	<0.4 mmol/L	<0.5 – 0.4 mmol/L	---
Total serum Ca 2+ , high	>3.1 mmol/L	>2.9 – 3.1 mmol/L	---
Total serum Ca 2+ , low	<1.75 mmol/L	<2.0 – 1.75 mmol/L	---
Serum phosphorous	<0.6 mmol/L	<0.8 – 0.6 mmol/L	---
Serum HCO 3 	<11 mmol/L	<16 – 11 mmol/L	---

a Laboratory abnormalities may be confirmed immediately or at the next scheduled clinic visit based on investigator judgment.

**Abbreviations:** ALT = alanine aminotransferase, BUN = blood urea nitrogen, Ca2+ = calcium, CK = creatine kinase, GGT = gamma glutamyl transferase, HCO3 = bicarbonate, K+ = potassium, Mg2+ = magnesium, Na+ = sodium, ULN = upper limit of normal

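### SAP 5.7.2 does not clearly put dipstick urinalysis in the shift tables, and no planned table shows dipstick haematuria worsening from baseline within the abnormal range

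*SAP*

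**What the plan says.** The commitment is in Protocol 10.4.3: "Urinalysis data will be listed and summarized by treatment period and overall, and will be checked for changes from baseline over time". Protocol 7.8 lists the content: "Urinalysis will include analysis for pH, specific gravity, glucose, ketones, blood, protein, urobilinogen, bilirubin, nitrite, and leukocytes". Urine protein, creatinine and osmolality are also measured at the central laboratory.

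SAP 5.7.2 implements this in four steps:

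- By-visit summaries: "Hematological, serum biochemistry, adrenal laboratories, and urine data and their changes (only for continuous laboratory parameters) from baseline will be summarized by visit".
- Graded shifts: "Shift tables for hematology and biochemistry data will also be presented showing change in CTCAE severity grade from baseline to each visit".
- Ungraded shifts: "For parameters for which a CTCAE scale does not exist, shift tables will be presented showing change in results from baseline", with the categories normal, low and high, or alternatively abnormal. No laboratory panel is named.
- A summary of predefined abnormalities following SAP Table 2. The row beginning "Urine blood (by dipstick" puts 2+, 3+ and 4+ in three different action columns. No comparison with baseline is stated for any row.

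SAP 6.1 keeps only the last valid assessment when a visit window holds more than one. SAP 7 declares as removed only the 6-minute walk supportive analyses and the paired t-tests. SAP 1 gives the SAP precedence where it conflicts with the protocol.

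**The concern.** Laboratory abnormalities are part of the primary endpoint, and the kidney has its own monitoring plan. Protocol 13.2.4 names urine blood as a decision marker. Unlike urine protein, it has no planned continuous measure. In a single-arm extension, each boy's comparison with his own baseline is the main internal evidence of a drug effect.

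If the tables show only how many boys sit at each level, a boy who had 4+ blood at entry looks the same as one who reached 4+ on treatment. If the only shift is normal versus abnormal, a boy who crosses from Table 2's continue column to its immediate-stop column appears unchanged.

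**Working it through.** The plan states no figure on this point, so there is none to reproduce. The check sets the planned outputs side by side, then bounds what by-visit counts alone can reveal.

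**Step 1. Does the ungraded shift sentence cover dipstick results?** It can be read two ways.

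- Narrow: it continues the preceding sentence, which names only hematology and biochemistry, so dipstick urine is left out.
- Broad: it covers every parameter lacking a CTCAE scale. Two things favour this. The abnormal alternative suits qualitative results, and the parallel protocol rule ("For parameters for which a CTCAE scale does not exist, the frequency of patients with values below, within, and above the normal ranges") stands in a paragraph covering serum biochemistry and urine data.

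The broad reading is the more plausible one, but the SAP does not settle it.

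**Step 2. What would each output show for urine blood?** I assume that 2+ and above counts as abnormal; the SAP sets no cut-off for the shift table.

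| Course | Normal/abnormal shift (broad reading) | Table 2 summary | Graded shift (not planned) |
|---|---|---|---|
| Negative, then 2+ | normal to abnormal | 2+ | negative to 2+ |
| 2+, then 4+ | abnormal to abnormal | 4+ | 2+ to 4+ |
| 4+, then 4+ | abnormal to abnormal | 4+ | 4+ to 4+ |
| Negative, then 4+, then a negative repeat in the same window | normal to normal | 4+ only if all assessments are used, which is not stated | negative to 4+ (worst value) |

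The second and third rows cannot be told apart in any planned table under the broad reading. Under the narrow reading the first column disappears as well.

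**Step 3. Can a repeat fall in the same window?** The Week 24 visit falls on study day 24 × 7 + 1 = 169, or as late as 169 + 7 = 176 with the visit tolerance. The Week 24 window closes at day 210. That leaves at least 210 − 176 = 34 days in which a repeat test replaces the scheduled value. The Table 2 footnote allows immediate confirmation, so such repeats are to be expected.

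**Step 4. Narrow reading only: what do by-visit percentages leave open?** With N boys, proportion p0 abnormal at baseline and p1 at a visit, the number newly abnormal lies between N × max(0, p1 − p0) and N × min(p1, 1 − p0). I use N = 220, the approximate upper bound in SAP 3.4. The prevalences are assumptions; the documents give none.

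| p0 | p1 | Newly abnormal boys |
|---|---|---|
| 5% | 5% | 0 to 11 |
| 10% | 10% | 0 to 22 |
| 20% | 20% | 0 to 44 |
| 5% | 10% | 11 to 22 |

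A normal/abnormal shift table would replace each range with an exact count of new onset. It would still not show worsening within abnormal.

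**The case against.** The strongest reply is that the SAP already offers several routes.

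- **New onset.** On the broad reading, new haematuria is tabulated. A reader might infer that dipstick urine has no usable comparison with baseline at all. The documents do not support that, because the ungraded shift sentence plausibly supplies one. For the same reason the 0 to 22 range is not the size of the problem: it applies only if no urinalysis shift table is produced. This part of the reply stands.
- **Proteinuria.** A reader might extend the point to urine protein. That fails. Protocol 13.2.4 plans quantitative ratios, the underlying measures are continuous and so qualify for change from baseline, and Table 2 sets thresholds for both ratios.
- **Adverse events.** A high dipstick result calls for a work-up. A work-up beyond a repeat test makes the abnormality reportable, and a TEAE must occur or worsen after first dose. SAP 5.7.1 tabulates renal events leading to special evaluation. This helps but does not close the gap. Under Protocol 8.1.1, results that need no intervention or further investigation are not reported as adverse events, and neither are those tied to an event already reported. Capture therefore depends on investigator action.
- **Listings.** They hold every value but do not summarise change.
- **Departure from protocol.** A reader might infer that the SAP silently dropped the commitment. Protocol 10.4.3 promises a check for change, not a graded shift table, so the documents show an unclear implementation rather than a proven departure.
- **Baseline.** Boys previously on ataluren enter the extension already on drug, so a shift from this baseline does not isolate onset on ataluren for them. This is correct, and the fix allows for it.

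**Conclusion.** The point holds as a minor one. SAP 5.7.2 leaves it unclear whether the shift tables include dipstick urinalysis. On either reading, no planned table shows dipstick haematuria worsening from baseline within the abnormal range, and a transient high value can be lost from by-visit tables. This falls short of what a reader would expect from the protocol's commitment to check urinalysis for change.

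The gap is limited to one renal marker. No sample size, test or stated conclusion depends on it. The verdict rests on the wording of SAP 5.7.2, Table 2 and SAP 6.1, and on the assumption that 2+ and above would be classed as abnormal.

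**What to change.** - In SAP 5.7.2, state that the shift tables for parameters without a CTCAE scale include urinalysis.
- For urine blood, add a shift table by reported dipstick grade, from baseline to each visit and from baseline to the worst post-baseline value. Take the worst value from all assessments, not only the last in each window.
- In the Table 2 summary row for urine blood, also count boys whose category is new or higher than at baseline.
- Show these tables by prior arm (ataluren/ataluren and placebo/ataluren, the grouping SAP 5.8.4 already uses), because the extension baseline is on drug for the first group.

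A graded shift for every other dipstick item is not needed. The cost is a few sentences in the SAP and a few extra tables from data already scheduled at every visit. No clinical rule or data collection changes.

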## **5. STATISTICAL ANALYSIS**

### **5.1. General Statistical Considerations**

Summary tables for continuous variables will contain the following statistics: n, mean, standard deviation, standard error, 95% confidence intervals (CIs) on the mean, median, minimum, and maximum. Summary tables for categorical variables will include N, n, and percentages. In by-visit summaries, the analysis visits will be derived via visit mapping windows.

For descriptive summary tables, the all data will be analyzed and displayed by ambulatory status (ambulatory or non-ambulatory) at baseline, unless specified otherwise. Where applicable, the summary data (mean, standard error) will be presented in graphical form of against time of visit.

By-patient listings will be created for each CRF module. The data will be listed by center/subject ID and visit.

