## 6. DATA HANDLING

### 6.1. Analysis Visits based on Visit Windows

Since some subjects had early terminations or unscheduled visits in during, the derived analysis visits will be generated by visit window defined as follows. For the 6 weeks post-treatment visit, assign AVISITN=14 and AVISIT=6-Weeks Post-Treatment.

Let Study day=assessment date –first dose date +1.

Study Day	AVISITN	AVISIT
Study Event='SCR' or < study day $\leq$ 1	1	Baseline
1 < study day $\leq$ 126	2	Week 12
126 < study day $\leq$ 210	3	Week 24
210 < study day $\leq$ 294	4	Week 36
294 < study day $\leq$ 378	5	Week 48
378 < study day $\leq$ 462	6	Week 60
462 < study day $\leq$ 546	7	Week 72
546 < study day $\leq$ 630	8	Week 84
630 < study day $\leq$ 714	9	Week 96
714 < study day $\leq$ 798	10	Week 108
798 < study day $\leq$ 882	11	Week 120
882 < study day $\leq$ 966	12	Week 132
966 < study day	13	Week 144

If there are more than 1 valid assessment within one visit window, the last one will be chosen as the analysis value.

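### SAP 5.7.2 omits, without declaring it, the worst-CTCAE-grade-per-patient laboratory tables planned in Protocol 10.4.3, and its by-visit shift tables let a prompt repeat replace an abnormal value

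*SAP*

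**What the plan says.** **Protocol 10.4.3** commits to grading and to a per-patient display. For hematology: "Hematological data will be graded according to CTCAE severity grade". It continues: "The frequencies of the worst severity grade observed will be displayed by worst CTCAE grade within a patient". The same section plans worst-grade-within-patient frequencies for those serum biochemistry and urine variables that have a CTCAE scale.

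**SAP 5.7.2** lists three laboratory outputs:

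- values and changes from baseline, by visit;
- shift tables: "Shift tables for hematology and biochemistry data will also be presented showing change in CTCAE severity grade from baseline to each visit" (with normal/low/high shifts where no CTCAE scale exists);
- threshold abnormalities: "Summary of abnormalities in laboratory variables pre-defined for safety monitoring will be done per the following Table 2".

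None is a worst-grade-per-patient table, and the CTCAE-grade shift tables name hematology and biochemistry but not urine.

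**Which values feed the by-visit tables.** SAP 5.1: "In by-visit summaries, the analysis visits will be derived via visit mapping windows". SAP 6.1 explains why: "Since some subjects had early terminations or unscheduled visits in during, the derived analysis visits will be generated by visit window". It then sets the tie rule: "If there are more than 1 valid assessment within one visit window, the last one will be chosen as the analysis value". No exception is made for safety data.

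**Repeat testing.** Footnote a to Table 2: "Laboratory abnormalities may be confirmed immediately or at the next scheduled clinic visit based on investigator judgment".

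**Declared changes.** SAP Section 7 lists two: removal of the supportive 6-minute walk analyses and of all paired t-tests. Neither concerns laboratory data.

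**The concern.** The primary endpoint (SAP 3.3) covers the frequency and severity of laboratory abnormalities as well as adverse events. The natural summary is how many boys ever reached each grade on treatment, and that is what the protocol planned. An analyst working from SAP 5.7.2 would not produce it, and a reader of Section 7 would not know it had gone.

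The by-visit shift tables are not a substitute, for two reasons. First, the same boy can appear in several of them, so they cannot be added up to a count of boys. Second, the last-value rule means that a transient abnormality followed by a prompt lower repeat is shown at the lower grade. Most exposed are abnormalities that were repeated quickly and led to no further work-up, because these also stay out of adverse-event reporting.

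**Working it through.** **1. Planned output against SAP output**

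| Data | Protocol 10.4.3 | SAP 5.7.2 |
|---|---|---|
| Hematology | Worst CTCAE grade per patient | Grade shift to each visit |
| Biochemistry, CTCAE-graded | Worst CTCAE grade per patient | Grade shift to each visit; Table 2 summary for selected parameters |
| Urine, CTCAE-graded | Worst CTCAE grade per patient | By-visit summary; Table 2 summary for selected parameters |

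The SAP applies a highest-severity-per-subject rule to adverse events (5.7.1) but does not carry it to laboratory values.

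**2. How long each window stays open after a scheduled visit**

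Inputs: study day = assessment date − first dose date + 1 (SAP 6.1), so nominal Week *w* falls on day 7*w* + 1; visit tolerance ±7 days (SAP Table 1); upper window limits from SAP 6.1. Days left = window end − visit day.

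| Week | Nominal day | Window end | Visit 7 days late | On time | 7 days early |
|---|---|---|---|---|---|
| 12 | 85 | 126 | 126 − 92 = 34 | 126 − 85 = 41 | 126 − 78 = 48 |
| 24 | 169 | 210 | 210 − 176 = 34 | 210 − 169 = 41 | 210 − 162 = 48 |
| 132 | 925 | 966 | 966 − 932 = 34 | 966 − 925 = 41 | 966 − 918 = 48 |

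All 11 closed post-baseline windows (Weeks 12 to 132) give the same three results. The Week 144 window has no upper limit, apart from the separately assigned post-treatment visit. Scheduled visits are 84 ± 14 = 70 to 98 days apart, so a confirmation left to the next scheduled visit falls in the next window and replaces nothing.

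A repeat within 34 days of an in-tolerance visit therefore always shares its window and, if it is the last value there, becomes the analysis value. The shown grade falls if the repeat is lower, is unchanged if equal, and rises if higher.

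**3. What Table 2 covers**

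Rows: 3 hepatic + 6 renal + 10 electrolyte = 19. Protocol 7.6 lists 8 hematology items; none is in Table 2.

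**4. Size of the replacement effect (assumed rates)**

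Let *q* be the share of abnormal scheduled values repeated inside the window and *r* the share of those whose last value has a lower grade. The documents give neither. The share lost from that visit's table at its grade is *q* × *r*:

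- 0.25 × 0.25 = 6%
- 0.50 × 0.50 = 25%
- 0.75 × 0.75 = 56%
- *q* = 0 (all confirmation at the next visit) gives 0%

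This is a gross loss, before any offset from later higher values.

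**5. Patients rather than values (illustration, assumed rates)**

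Take 12 post-baseline windows and 220 boys, the upper bound in SAP 3.4, and an independent isolated Grade ≥3 value with probability *p* = 0.5% per window. A worst-grade table would show 1 − (1 − 0.005)^12 = 5.8%, or 12.8 boys. If half of these values were replaced by a normal repeat, 1 − (1 − 0.0025)^12 = 3.0%, or about 6.5 boys, would still appear somewhere, spread over 12 tables at 220 × 0.0025 = 0.55 per table. At *p* = 0.2% and 1% the worst-grade counts are 5.2 and 25.0, and the counts still visible are 2.6 and 12.8. Early termination would lower all of these.

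**The case against.** The omission and the window arithmetic are not in dispute. The case on the other side is that the practical loss is small.

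- **Table 2 may escape the last-value rule.** Its summary is not described as by-visit, so it may count every qualifying value, and it covers the main hepatic and renal signals. That is a fair reading, but the SAP does not say so, and hematology is outside Table 2 either way.
- **The repeat-testing footnote belongs to Table 2.** For hematology the documents set no repeat schedule and leave evaluation to the investigator. This stands: replacement is best documented where another summary exists. The missing per-patient count does not depend on it.
- **Adverse-event tables give a worst-grade display.** Laboratory abnormalities reported as TEAEs are tabulated by highest severity per subject, with a separate Grade ≥3 table, and Protocol 6.3.1 says Grade 3–4 abnormalities should in general count as clinically significant. An abnormality that stops study drug under Table 2 also triggers work-up and so is largely captured. This stands for those events. However, Protocol 8.1.1 keeps abnormalities that need only a confirmatory repeat out of adverse-event reporting.
- **Listings are planned.** They preserve every value but give no frequencies.
- **The protocol table may survive.** SAP 1 gives the SAP precedence only where the two conflict, and silence need not be conflict. This is arguable, but it leaves the analyst to guess.
- **The 6–56% range is assumed.** Correct. It counts values at a visit, not boys, and may be 0%.
- **Not all 8 hematology items need have a CTCAE scale.** Also correct; the documents do not say which do.

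**Conclusion.** The concern holds and should be fixed. Three things follow from the documents alone: the protocol's worst-grade-per-patient tables are absent from SAP 5.7.2; Section 7 does not declare this; and any repeat made within 34 to 48 days of a scheduled visit, depending on visit timing, takes that visit's place in the shift tables if it is the last value in the window. As written, no SAP table gives the share of boys who ever reached a given CTCAE grade in hematology, and the same gap exists for CTCAE-graded biochemistry outside Table 2.

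The size of any understatement is not known. The range of 6–56% of abnormal scheduled values rests on assumed repeat and improvement rates of 25–75% each, with 0% if no confirmation is done inside the window. The study is descriptive and the values remain in the listings, so this is a reporting gap in a primary safety output, not a loss of data.

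**What to change.** In SAP 5.7.2:

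1. Restore the frequency of the worst post-baseline CTCAE grade per patient for hematology and for CTCAE-graded biochemistry and urine variables, using all scheduled and unscheduled values from first dose to 6 weeks after last dose. This matches the treatment-emergent period in SAP 5.7.1.
2. Present it as a shift from baseline grade to worst grade. This shift and the stated time limits go slightly beyond Protocol 10.4.3, but they make the table interpretable.
3. State that the Table 2 summary uses all post-baseline values.
4. Keep the last-value rule of SAP 6.1 for by-visit summaries only.
5. Declare in Section 7 any departure from Protocol 10.4.3 that remains.

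The cost is SAP wording and programming on data already held. The result is a few more tables and, probably, somewhat less favourable abnormality rates. No clinical rule changes.
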